In this study, we will utilize non-invasive PET imaging to assess vascular/plaque and myocardial inflammation. A recent review article nicely summarizes the utility of PET in the setting of ACS [33]. The strength of PET-guided imaging in this setting is the identification of activated inflammatory cells in the atherosclerotic plaque, providing important information regarding the mechanism of vascular instability. Furthermore, longitudinal PET studies can assess the effectiveness of potentially novel anti-inflammatory therapies, such as evolocumab. Initial validation of FDG-PET imaging in the setting of ACS was performed in mice [34], but other reports also provide proof of feasibility in large animals and humans [35, 36]. Ripschler et al. subsequently demonstrated that the extent of FDG-derived myocardial inflammation early after myocardial infarction correlated with infarct size and systemic inflammatory markers at that time and with left ventricular ejection fraction and cardiac volumes at 6-9 month follow-up [37].

The multimodality dal-PLAQUE imaging study successfully utilized FDG-PET to assess plaque inflammation and burden in patients with a high risk of coronary heart disease [38]. A subsequent study reported a functional alteration of the plaque, characterized by activation of resident inflammatory cells, which can cause plaque instability and occlusive thrombus formation [39]. Since persistent activation of adaptive immunity in patients with unstable angina is linked to

coronary instability [40], we propose to evaluate the impact of evolocumab on the extent and degree of vascular inflammation as well in our study cohort.

4. Study Procedures (for the intervention study group)

a. Study design, including the sequence and timing of study procedures (distinguish research procedures from those that are part of routine care).

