- b. Obtaining remnant samples from blood draws in the ED:
 - i. After a patient agrees to participate and signs the ICF, we will access the JHH remnant sample repository to obtain remnant blood from the earliest timepoint at hospital presentation. We will work with the JHBMC Pathology Department to locate and retrieve the samples for analysis of the proposed biomarkers.

5. Inclusion/Exclusion Criteria

- **5.1 Inclusion Criteria** (for the intervention study group)
 - a. Age 25 to 90 years.
 - b. Non-ST-elevation and ST elevation myocardial infarction, with compatible symptoms and ECG changes.
 - c. Permission of attending physician.
 - d. Ability to understand the risk, benefits, and alternatives of participation.
 - e. Ability to administer study drug within one week of hospital presentation.

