Previously published clinically relevant, drug-induced TBR changes are reported in the range of 5%-15%. [44] The power calculations for a 10% and 15% TBR difference based on a sample size of 50 patients per study arm are outlined in Table 3 below. Table 1 uses a 1-sided p-value of 0.05, under the hypothesis that evolocumab will lower inflammation and will not raise it,

consistent with the approach used in the Dal-PLAQUE study. Calculations are performed using non-parametric statistics accounting for the possibility of non-normally distributed TBR data.

Tables 3: Power calculations using a 1-sided p-value, i.e. only assumes that PCSK9 inhibition will lower TBR in the most diseased segment (MDS) and will not raise TBR.

Table 3			Estimated	Detectable
	N in each group	Median (IQR)	Power at	Point
		TBR in STEMI	10% & 15%	Estimate at
		Population at 30	TBR	70% &
		days	Difference	80% Power
Aorta	N = 50	3.2(2.7-4.0)	88%	-8.1%
MDS			99%	-9.1%
Carotid	N = 50	2.5 (2.1 – 3.0)	97%	-6.4%
MDS			99%	-7.2%

The table above shows good to excellent power to demonstrate a difference of 10%, and an excellent power to show a difference of 15% in the primary outcome.

Mean and standard deviations of anticipated TBR in STEMI population at 30-days:

 \triangleright Aorta MDS: 3.3 ± 0.6

 \triangleright Carotid artery MDS: 2.6 ± 0.4

Since the timepoint of study drug administration may vary between participants hospitalized at JHH and Bayview, we will create a co-variable to document the time period between hospitalization and study drug administration and adjust our analysis accordingly.

Sample Size Considerations (for the observation study group)

Analysis of Lp(a) in 37 patients in the placebo group of the intervention study indicates an increase in Lp(a) (median, IQR) from 64 [41,187] to 82 [37,265] nmol/L from that obtained during the hospitalization and at 30 days. We would like to obtain an earlier value and correlate the findings with other inflammatory markers and mediators. Given the findings in the above analysis, we believe results in 100 additional patients would provide an adequate sample size.

a. Early stopping rules.

The DSMB will perform any interim analysis they require to monitor patient safety and provide reports advising continuation of the study.

10. Study Statistics (observation study):

Statistical Approach

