Evolocumab in Patients With Acute MI NCT04082442 7/14/2021

Evolocumab in Patients with Acute Myocardial Infarction (NCT04082442)

Study Statistics

Cover Sheet

Title: Evolocumab in Patients with Acute Myocardial Infarction: A Double-blind, Prospective, Randomized, Placebo-Controlled Study

Study Type: Interventional (Randomized, Double-Blind, Placebo-Controlled)

Population: Patients with acute myocardial infarction receiving high-intensity statin therapy

Sample Size: 100 participants (50 per arm: Evolocumab vs. Placebo)

Primary Outcome: Percent change in LDL-cholesterol (LDL-C) from baseline to 30 days

Key Secondary Outcome: Change in myocardial inflammation measured by FDG-PET (mean Standardized Uptake Value, SUV) from baseline to 30 days

Analysis Population: All randomized participants with evaluable baseline and follow-up data

Primary Endpoint Analysis

Endpoint Definition: Difference in the mean percent change in LDL-C from baseline (prerandomization) to 30 days in the evolocumab and placebo groups.

Statistical Method:

- Mean ± SD LDL-C at baseline and 30 days will be summarized for each group.
- Between-group comparisons will use an independent-samples t-test (two-sample test of means).
- Percent change will be calculated as: ((LDL-C30d LDL-Cbaseline) / LDL-Cbaseline) × 100.
- Two-sided p < 0.05 will indicate statistical significance.
- Results will also be presented as mean differences with 95% confidence intervals.

Power Considerations: Assuming baseline LDL-C \approx 110 mg/dL, 50% reduction with standard statin therapy, and an additional 50% reduction with evolocumab, a sample size of 50 per group provides >99% power (one-sided α = 0.05) to detect a 13.5 mg/dL absolute LDL-C difference.

Secondary Endpoint Analysis

Endpoint Definition: Change in inflammation quantified as mean FDG-PET Standardized Uptake Value (SUV) from baseline (index hospitalization) to 30 days in the evolocumab and placebo groups.

Statistical Method:

- For within-group change: paired t-test or Wilcoxon signed-rank test (if non-normal).
- For between-group comparisons: independent-samples t-test or Mann-Whitney U test.
- Data will be presented as mean ± SD and mean difference (95% CI).
- Significance defined as two-sided p < 0.05.

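### The myocardial FDG-PET comparison is planned without covariates, although MI type, pre-randomization troponin and the protocol's own time-to-drug covariate are available; the gain is precision only and its size is unknown

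*SAP*

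**What the plan says.** **Outcome and test.** The SAP's Secondary Endpoint Analysis defines the outcome as "Change in inflammation quantified as mean FDG-PET Standardized Uptake Value (SUV) from baseline (index hospitalization) to 30 days"; the SAP cover sheet specifies myocardial inflammation. The arms are compared by "For between-group comparisons: independent-samples t-test or Mann-Whitney U test", and the error rate is "Significance defined as two-sided p < 0.05". No covariate or stratum is named.

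**Population.** Protocol 5.1(b) admits "Non-ST-elevation and ST elevation myocardial infarction, with compatible symptoms and ECG changes". No stratification of the randomization by MI type is described.

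**Prognostic information.** Protocol Section 3 cites a study in which "the extent of FDG-derived myocardial inflammation early after myocardial infarction correlated with infarct size and systemic inflammatory markers at that time". Protocol 2.2 a lists troponin (item xii) among the markers sampled before randomization. MI type is known at entry.

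**Adjustment already promised.** Protocol Section 9, just after the TBR planning values, notes that dosing time may differ between the two hospitals and commits to a covariate for the interval from hospitalization to study drug. It does not say which outcomes this covers.

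**TBR power.** Table 3 is introduced as "Power calculations using a 1-sided p-value, i.e. only assumes that PCSK9 inhibition will lower TBR", and its means and SDs appear under "Mean and standard deviations of anticipated TBR in STEMI population at 30-days". The SAP repeats the resulting power (above 88% to 99% for differences of 10% to 15%) without either qualification.

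**The concern.** A t-test or rank test leaves in the error term any variation in PET uptake that is predictable at entry. By the protocol's own account infarct size is one source of that variation. MI type and pre-randomization troponin are plausible, already recorded proxies for it, and both precede dosing. The first PET scan is a less clean covariate. Protocol 2.2 b i distinguishes participants by whether that scan fell within 48 hours of study drug, and Section 4a lets it be done after discharge, so it may follow the dose.

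The two documents also disagree. Neither SAP test can take a continuous covariate, so the adjustment promised in Protocol Section 9 cannot be delivered as the SAP stands.

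At stake is the precision of the trial's main mechanistic question. A smaller matter is that a reader of the SAP would take the TBR power as applying to the enrolled population and to the SAP's two-sided test. It was computed for neither.

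**Working it through.** **1. Reproduce the stated myocardial power.** Inputs: mean 35.4, SD 18.1, a 30% difference and 50 per arm (Protocol Section 9; SAP power paragraph); two-sided 0.05 (SAP).

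- Difference = 0.30 × 35.4 = 10.62.
- Standard error = 18.1 × √(2/50) = 18.1 × 0.2 = 3.62.
- Noncentrality = 10.62 / 3.62 = 2.934.
- Normal approximation: Φ(2.934 − 1.960) = Φ(0.974) = 83.5%.
- Noncentral t, 98 df: 82.8%.
- Mann-Whitney, taking relative efficiency 0.955: 81.0%.

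The stated 80% is reproduced, slightly on the conservative side.

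**2. Add the covariates.** If they explain a share R² of the outcome variance, the residual SD is 18.1 × √(1 − R²). Three covariates (MI type, log troponin, time to drug) leave 95 df. R² is not in the documents, so the range below is an assumption.

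| R² | Residual SD | Noncentrality | Power, two-sided |
|---|---|---|---|
| unadjusted | 18.10 | 2.934 | 82.8% |
| 0 | 18.10 | 2.934 | 82.7% |
| 0.10 | 17.17 | 3.092 | 86.5% |
| 0.20 | 16.19 | 3.280 | 90.1% |
| 0.30 | 15.14 | 3.506 | 93.5% |

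If the covariates explain nothing, the cost is about 0.1 point. Two covariates (96 df) give the same figures to one decimal.

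**3. Check validity.** A simulation with two covariates (MI type at a 50:50 mix and a continuous marker; 50 per arm; 4,000 runs per setting) gave type I error of 4.5% to 5.3% both with and without adjustment.

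**4. What the SD stands for.** The 18.1 describes a level, while the SAP tests a change. For equal SDs at both scans and between-scan correlation ρ, the SD of the change is 18.1 × √(2(1 − ρ)), which equals 18.1 only when ρ = 0.5. The documents give no ρ, so the table illustrates the gain and does not forecast the trial's power.

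**5. TBR, treated separately.** Inputs: aorta mean 3.3, SD 0.6 (Protocol Section 9); 50 per arm; a 10% difference = 0.33.

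- Noncentrality = 0.33 / (0.6 × 0.2) = 2.75.
- One-sided: Φ(2.75 − 1.645) = 86.5%. Table 3 states 88%, so it is approximately reproduced.
- Two-sided, as in the SAP: Φ(2.75 − 1.960) = 78.5%; noncentral t gives 77.7%.
- Carotid (2.6, SD 0.4), noncentrality 0.26 / 0.08 = 3.25: one-sided 94.6% (stated 97%), two-sided 90.1%.

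**The case against.** The strongest reply is that nothing here is invalid. Randomization makes the unadjusted comparison unbiased and its error rate is correct, so adjustment is a preference about efficiency. That stands.

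Second, the support for the covariates is indirect. The cited correlation concerns uptake soon after infarction, whereas the SAP tests change to 30 days, and a change score already removes stable differences between patients. Dosing may occur up to a week after presentation (Protocol 5.1(e)), so pre-randomization troponin may be drawn at varying times and be a weaker marker of infarct size. This also stands, and it is why R² = 0 belongs in the table. A reader might infer that adjustment is certain to add power; the documents show only that it costs almost nothing.

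Third, a reader might infer that the STEMI-only label undermines the key secondary outcome, or that troponin should also sharpen the TBR analysis. Neither is supported. The label belongs to vascular TBR; the myocardial planning value is called an overall mean. Nothing in the documents ties infarct size, MI type or troponin to aortic or carotid TBR.

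Fourth, a reader might want to quantify the TBR power lost by mixing MI types. If half were NSTEMI with a mean TBR 10% to 20% lower, one-sided aortic power would fall from 86% to 80% to 70%. But the mix and the gap are both invented. Part of the fall arises only because 10% of a lower pooled mean is a smaller difference: with the SD held at 0.60, power is already 83% to 79%, and no covariate recovers that.

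**Conclusion.** The point holds as one of precision and of consistency between the documents. The SAP's myocardial PET test omits entry information that is already collected and that the protocol itself links to early uptake, and it cannot deliver the time-to-drug adjustment promised in Protocol Section 9. The effect on power at 50 per arm runs from a loss of about 0.1 point (R² = 0) to a gain of about 11 points (R² = 0.30), conditional on 18.1 being the SD of the analysed outcome. The documents fix neither quantity.

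It would be wrong to conclude that pooling STEMI and NSTEMI biases the comparison or inflates the false-positive rate.

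The TBR matter is one of labelling and sidedness. The SAP's figure rests on STEMI-only, one-sided planning values. With the listed mean and SD, two-sided aortic power for a 10% difference is about 78%. No figure for the STEMI/NSTEMI mix can be derived from the documents.

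**What to change.** **Myocardial PET.** Before PET data are analysed by arm, amend the SAP so that the main between-group comparison is a linear model of the change (or the log ratio of the two scans, if skewed) on:

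- arm;
- MI type (STEMI or NSTEMI);
- log pre-randomization troponin;
- time from hospitalization to study drug.

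Report the adjusted difference with its 95% confidence interval. State a simple rule for missing troponin that does not use arm, for example the overall mean of the log values. Keep the t-test or Mann-Whitney test as a sensitivity analysis. The deadline is worded this way because Protocol Section 9 already reports an Lp(a) analysis in 37 placebo patients of the intervention study, so some data have been looked at by arm.

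**Reconciliation.** State which outcomes the time-to-drug adjustment covers, so that the protocol and SAP agree.

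**TBR.** Say beside the SAP's TBR power that it rests on STEMI-only, one-sided planning values, and add the two-sided figure. Show any value for the enrolled mix as an assumption with a range.

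**Cost.** A few lines of SAP text and at most three degrees of freedom. MI type and troponin are already collected and the time variable is already planned, so no new data collection is needed.

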2.3 Exploratory

The exploratory basic science outcome is: Direct comparison of endothelial cell function in cells harvested from intravascular equipment or directly from patient serum in the evolocumab- and placebo-randomized patient groups.

The exploratory imaging outcomes are: To compare PET assessed myocardial and vascular inflammation in the evolocumab and placebo groups on the exams obtained during the hospitalization.

3. Background (briefly describe pre-clinical and clinical data, current experience with procedures, drug or device, and any other relevant information to justify the research)

According to the latest AHA fact sheet, over 400,000 Americans suffered a NSTEMI or a STEMI in 2017 [2]. Despite aggressive risk factor modification in these patients, recurrent ischemic events are frequent and are related to plaque burden and instability, platelet aggregation, and ongoing inflammation [3]. These patients have a high risk of short-term unfavorable outcomes, including mortality, and therefore may significantly benefit from an early intervention which would significantly decrease those risks [4]. Previous studies indicated an inflammatory environment in the acute infarct setting as indexed by high levels of hs-CRP, total white blood cell count and IL-6 [5]. Inflammation contributes to many of the characteristics of those plaques implicated in the pathogenesis of recurrent ischemic events [6]. The pathways which promote fibrous cap rupture involve inflammation [7] and excess lipid accumulation. In a large cohort of patients suffering a first myocardial infarction, new heart failure is associated with an increase in index hospitalization mortality and in those who develop heart failure following discharge. Short- and long- term mortality are significantly greater in those NSTEMI and STEMI patients who develop heart failure [8]. Inflammatory mediators are also activated in heart failure after acute myocardial infarction and are associated with progressive left ventricular dysfunction [9].

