- 2) Change in vascular inflammation from the FDG-PET scan obtained during the early post-infarct period and the 25-30 day FDG-PET scan in the evolocumab and placebo groups. Vascular inflammation will be assessed in the average of the TBR (target to background) of the MDS (of most diseased segments) of the carotid artery or aorta in the evolocumab vs. placebo groups. The target to blood pool ratio or TBR is the ratio of the mean activity in the vessel to the venous blood pool. [43]
- 3) Change in myocardial inflammation from the FDG-PET scan obtained during the index hospitalization and the thirty-day FDG-PET scan in the evolocumab and placebo groups.
- 4) Difference in the FDG-PET assessment of vascular inflammation in the MDS of carotid artery or aorta in the evolocumab versus placebo groups at 30 days.
- 5) Difference in the FDG-PET assessment of myocardial inflammation at 25-30 days in the evolocumab and placebo groups.
- 5) Serum markers of inflammation and of endothelial and platelet function in the two randomized groups at 25-30 days.
- 6) Change in serum markers of inflammation and of endothelial and platelet function in the two randomized groups from the index hospitalization to 25-30 days.

Secondary (for the observation study group)

1. Change in levels of inflammatory markers and mediators between the initial hospitalization, during hospitalization and 30-day follow-up

Sample Size Considerations (for the intervention study group)

We are providing power considerations for the primary as well as key secondary endpoints (see Tables 1-3).

Primary endpoints:

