For calculation of power for the co-primary endpoint of LDL-C, we anticipate median baseline presentation LDL-C of 110~(90-130)~mg/dL in our patient population. This number is informed by prior ACS trials as well as local experience with the STEMI population treated at the Johns Hopkins Hospital (with approximately 25%-35% of the population already on baseline statin therapy). We expect this LDL-C value to be reduced by approximately 50% by high intensity statin therapy in the standard treatment arm (i.e. to an LDL-C of 55 (40-70) mg/dL at 30 days). We anticipate a further 50% lowering of LDL-C at 30 days after the administration of evolocumab (i.e. to an LDL-C of 28 (14 – 42) mg/dL. As is shown below (Table 1), using a one-sided p-value of 0.05, the study has nearly 100% power to detect this difference, and will have 80% power to detect an absolute LDL-C reduction of only 13.5 mg/dL (24% reduction in LDL-C at 30 days). Additionally, Table 2 presents the expected mean \pm SD baseline and 30-day LDL-C levels and the expected percent changes in the mean LDL-C in the placebo and evolocumab arms.

Table 1:

		Anticipated	Estimated	Detectable
N in each group	Median (IQR)	Percent	Power to	Point
	LDL-C in ACS	LDL-C	Detect a	Estimate at
	Population at	Reduction in	50%	>80%
	baseline	the	Additional	Power
		Standard of	LDL	
		Care Arm	Lowering	
N = 50	110 (90-130)	50% (40 –	99+%	-13.5 mg/dL
		60%)		

Table 2: Expected mean \pm SD LDL-C levels at baseline and thirty-days and the percent change from baseline to 30 days in the placebo and evolocumab groups.

Groups:		LDL-C, mg/dl		% change from	
		Baseline, mean (SD)	30 day, mean (SD)	baseline, mean (SD)	
High	+Placebo	110 (±14)	55 (±11)	-50 (±12)	
dose statin	+Evolocum ab		28 (±10)	-75 (±14)	

For the co-primary FDG-PET assessed myocardial inflammation endpoint, appropriate data necessary for power calculations are currently unavailable. With 50 patients in each arm, applying the overall mean (SD) of 35.4 (18.1) from Ripschler et al [38] as a baseline estimate, we will have 80% power to detect a 30 % difference in FDG-PET assessed myocardial inflammation between the evolocumab and placebo groups.

Secondary Endpoint:

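### The key secondary PET endpoint is tested as an unadjusted change score; adjusting the 30-day value for the first scan is more precise, but the plain 30-day comparison must stay because some first scans can follow the dose

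*SAP*

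**What the plan says.** The SAP cover sheet names one key secondary outcome: "Key Secondary Outcome: Change in myocardial inflammation measured by FDG-PET (mean Standardized Uptake Value, SUV) from baseline to 30 days". Under Secondary Endpoint Analysis the between-arm method is "For between-group comparisons: independent-samples t-test or Mann-Whitney U test", with "Significance defined as two-sided p < 0.05". No model includes the first-scan value.

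Protocol section 9 (Secondary) lists the change in myocardial inflammation as item 3. It then lists the 30-day value by arm as the first of two items numbered 5: "Difference in the FDG-PET assessment of myocardial inflammation at 25-30 days in the evolocumab and placebo groups". Items 2 and 4 do the same for vascular TBR. Objectives 2.2b and 2.2c follow the same pattern.

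Two other provisions touch on the first scan:

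- Objective 2.2b(i) plans separate analyses by whether that scan fell within 48 hours of study drug.
- The sample size text in section 9 plans a covariate for the time from hospitalization to study drug. The SAP does not repeat it.

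Neither adjusts for first-scan SUV.

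The first scan need not be a pre-dose scan. Section 4a has the drug given in early hospitalization and lets some participants have the first scan as outpatients; section 4g puts the single dose on the day of enrollment. Section 2.3 adds an exploratory comparison of the arms "on the exams obtained during the hospitalization".

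**The concern.** A raw change score fixes the coefficient of the first scan at 1, whatever the data show. If the two scans are only moderately correlated, that adds noise. Below a correlation of 0.5 (with equal SDs) it is noisier than ignoring the first scan altogether. The more efficient use of the same scan is as a covariate.

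There is a second cost. If some first scans are taken after the dose and the drug acts early, the change score subtracts whatever effect is already visible. At stake are the power and the size of the estimate for the SAP's only named key secondary outcome. The LDL-C primary is not affected.

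**Working it through.** **Inputs from the documents.** Mean 35.4 and SD 18.1, taken at face value (protocol section 9; SAP power considerations). Both describe a single value, not a change. Difference 30%, so D = 0.30 × 35.4 = 10.62. 50 per arm, two-sided 5% (SAP).

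**Assumptions.** The correlation rho between first and 30-day scans, and the average fraction f of the 30-day effect already present on the first scan, are not in the documents and are shown as ranges. SDs are taken as equal at the two scans.

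**1. The plan's own figure.** Standard error = 18.1 × √(2/50) = 3.62, and 10.62/3.62 = 2.93. Power is 82.8% by noncentral t, or 81.0% for Mann-Whitney with an assumed relative efficiency of 0.955. The difference detectable at 80% power is 28.9% (t) or 29.6% (Mann-Whitney). The stated 80% for 30% therefore reproduces, but for a value at one time point. It holds for the change only if rho is about 0.46 or more.

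**2. Precision when the first scan carries no drug effect (f = 0).**

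- SD of change = 18.1 × √(2(1 − rho))
- Residual SD after adjustment for the first scan (ANCOVA) = 18.1 × √(1 − rho²)
- Variance ratio, change to ANCOVA = 2(1 − rho)/(1 − rho²) = 2/(1 + rho)
- Variance ratio, 30-day value to ANCOVA = 1/(1 − rho²)

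| rho | SD change | SD ANCOVA | Change/ANCOVA | 30-day/ANCOVA | Power: change | Power: 30-day | Power: ANCOVA |
|---|---|---|---|---|---|---|---|
| 0.3 | 21.42 | 17.27 | 1.54 | 1.10 | 69% | 83% | 86% |
| 0.5 | 18.10 | 15.68 | 1.33 | 1.33 | 83% | 83% | 92% |
| 0.7 | 14.02 | 12.93 | 1.18 | 1.96 | 96% | 83% | 98% |

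**3. When the first scan already carries part of the effect.** Expected estimates are D for the 30-day value, D(1 − f) for change and about D(1 − rho × f) for ANCOVA. Power at rho 0.3 / 0.5 / 0.7:

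| f | Change | ANCOVA | 30-day value |
|---|---|---|---|
| 1/3 | 37 / 49 / 70% | 78 / 80 / 88% | 83% |
| 1/2 | 23 / 31 / 47% | 73 / 71 / 75% | 83% |

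At f = 1/3 change estimates 7.08 of 10.62. ANCOVA estimates 9.56, 8.85 and 8.14, a loss of 10%, 17% and 23%. The 30-day value keeps all 10.62.

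Simulation (2,000 runs, rho 0.5, f 0.5) gave mean estimates of 10.59 (30-day), 5.30 (change) and 7.95 (ANCOVA), against expected values of 10.62, 5.31 and 7.96.

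**4. ANCOVA against the 30-day value.** ANCOVA has more power only if D(1 − rho × f)/√(1 − rho²) exceeds D, that is, if f < (1 − √(1 − rho²))/rho. The limits are 0.15, 0.27 and 0.41 at rho 0.3, 0.5 and 0.7.

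**The case against.** If every first scan preceded the dose, the two-sample test of change would be valid and unbiased, and the point would be one of efficiency alone. At rho 0.7 the gain is only from 96% to 98%. Both rho and f are assumed, and the documents show that post-dose first scans can occur, not that an early drug effect exists. All of this stands, and it limits the size of the point.

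Three stronger readings are tempting, and the documents do not support them.

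- **That both planned contrasts subtract an early effect.** Only the change score does. The 30-day comparison in protocol section 9 keeps the full effect; its weakness is precision alone.
- **That ANCOVA settles the matter, so the 30-day comparison can become descriptive.** A post-dose first scan is itself a post-treatment variable. Adjusting for it still removes about rho × f of the effect, and beyond the limits in step 4 it has less power than the plain comparison the protocol already lists.
- **That the trial's answer is left open because both contrasts are planned.** The SAP cover sheet names the change in myocardial SUV as the one key secondary outcome, and the 30-day value is a further secondary.

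It is also fair to say that the protocol gives thought to scan and dose timing, through the 48-hour split and the time-to-drug covariate. Neither uses the first-scan SUV, so neither recovers the lost precision.

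**Conclusion.** The point holds as an inexpensive improvement to the key secondary analysis, not as a flaw that invalidates it. In every case computed here (rho 0.3 to 0.7, f from 0 to one half) the first-scan-adjusted model has more power than the change test and loses less of any early effect. With no early effect, the change test needs 1.54, 1.33 and 1.18 times as many patients as ANCOVA at rho 0.3, 0.5 and 0.7.

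The adjusted model does not dominate the unadjusted 30-day comparison once first scans carry a drug effect, so it should replace the change test and not the 30-day test. The variance ratios rest on equal SDs at the two scans; the power figures also take the plan's 18.1 and 10.62 at face value. A reader should not infer that an early effect has been shown.

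**What to change.** In the SAP, under Secondary Endpoint Analysis:

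1. Replace the two-sample test of change with a linear model of 30-day SUV on arm, with first-scan SUV as covariate. Report the adjusted mean difference with its 95% CI at two-sided 5%. Use the same model for TBR.
2. Keep the between-arm comparison of the 30-day value in all patients with a 30-day scan, adjusted only for covariates measured before the dose. Make it a formal companion analysis with an estimate, interval and test, because it is the contrast that a post-dose first scan cannot attenuate.
3. Report raw change descriptively.

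The cost is one SAP paragraph. No new data are needed: the adjusted model uses the same paired scans as the change score. The remaining downside is some attenuation of the adjusted estimate where first scans follow dosing, which the companion analysis would help to reveal.

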Power Considerations: Assuming mean \pm SD = 35.4 \pm 18.1 (Ripschler et al.), with 50 participants per arm, there is 80% power to detect a 30% difference in mean SUV between groups. For vascular inflammation (TBR, target-to-background ratio), published differences of 10–15% yield >88–99% power for n = 50 per group.

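### The SAP gives the published TBR range as 10–15% where the protocol gives 5–15%, and quotes one-sided power beside a two-sided test; two-sided power at 5% is about 28% (aorta) and 36% (carotid)

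*SAP*

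**What the plan says.** **SAP, Secondary Endpoint Analysis, Power Considerations.** On vascular TBR the SAP has one clause: "published differences of 10–15% yield >88–99% power for n = 50 per group". It names neither the vessel nor the sidedness, and it gives no detectable difference. The Statistical Method list in the same section has "Significance defined as two-sided p < 0.05". The cover sheet gives the size as "100 participants (50 per arm: Evolocumab vs. Placebo").

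**Protocol, section 9, Sample Size Considerations (intervention study group), Secondary Endpoint.** The paragraph opens: "Previously published clinically relevant, drug-induced TBR changes are reported in the range of 5%-15" per cent. It then introduces "The power calculations for a 10% and 15% TBR difference based on a sample size of 50 patients per study arm". The caption of Table 3 reads "Power calculations using a 1-sided p-value, i.e. only assumes that PCSK9 inhibition will lower TBR", and the text above it says "Table 1 uses a 1-sided p-value of 0.05, under the hypothesis that evolocumab will lower inflammation". That sentence names Table 1, but the hypothesis it describes is the TBR one.

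Table 3 gives, for 50 per group:

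| Vessel (most diseased segment) | Power at 10% | Power at 15% | Detectable at 70% power | Detectable at 80% power |
|---|---|---|---|---|
| Aorta | 88% | 99% | 8.1% | 9.1% |
| Carotid | 97% | 99% | 6.4% | 7.2% |

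Below the table the protocol lists the anticipated 30-day values: "Aorta MDS: 3.3 ± 0.6", and 2.6 ± 0.4 for the carotid.

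**The concern.** The SAP attaches the word published to the two effect sizes that the protocol chose for its power table. The protocol's published range starts at 5%, and nothing in either document supports 10–15% as the range in the literature. Someone with only the SAP would conclude that the trial has at least 88% power for any effect of published size.

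The quoted power also comes from a one-sided calculation, and the SAP sets a two-sided criterion. Even at 10%, then, the stated figure does not describe the planned test.

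What is at stake is how the vascular result is read. Change in TBR and TBR at 30 days are both listed secondary outcomes in protocol section 9. If the 30-day comparison is not significant, the SAP's sentence invites the reading that an effect of published size has been ruled out. At the 5% end, which the protocol calls clinically relevant, the design cannot support that.

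**Working it through.** **Inputs.** 50 per arm (SAP cover sheet; protocol Table 3). Means and SDs at 30 days: aorta 3.3 and 0.6, carotid 2.6 and 0.4 (protocol, below Table 3). Alpha 0.05, one-sided for the protocol's calculation and two-sided for the SAP's analysis.

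**Formula.** Two-sample t-test. Standardised difference d = (relative difference × mean) / SD. Noncentrality = d × √(50/2) = 5d, with 98 degrees of freedom.

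- Aorta: d = 0.05 × 3.3 / 0.6 = 0.275 at 5%; 0.55 at 10%; 0.825 at 15%.
- Carotid: d = 0.05 × 2.6 / 0.4 = 0.325 at 5%; 0.65 at 10%; 0.975 at 15%.

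**Step 1: reproduce the plan's figures (one-sided 0.05).** Aorta: 86% at 10% and 99% at 15%, against 88% and 99% in Table 3. Carotid: 94% and >99%, against 97% and 99%. The protocol says it used non-parametric methods. A simulated one-sided Mann-Whitney test on log-normal data gives 87.9% (aorta) and 95.6% (carotid) at 10%, closer to the table. The one-sided 80%-power detectable difference is 9.1% for the aorta, equal to Table 3, and 7.7% for the carotid, against 7.2%. So the quoted figures are one-sided, and the listed SDs are close to those behind Table 3.

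**Step 2: power across the protocol's range.**

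| Difference | Aorta, one-sided | Aorta, two-sided | Carotid, one-sided | Carotid, two-sided |
|---|---|---|---|---|
| 5% | 39% | 28% | 49% | 36% |
| 7.5% | 66% | 53% | 78% | 67% |
| 10% | 86% | 78% | 94% | 90% |
| 15% | 99% | 98% | >99% | >99% |

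**Step 3: cross-check at 5% from Table 3 alone.** At 80% one-sided power the expected z is 1.645 + 0.842 = 2.487. Scale it to a 5% difference:

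- Aorta: (5/9.1) × 2.487 = 1.366. Φ(1.366 − 1.645) = 39% one-sided; Φ(1.366 − 1.96) = 28% two-sided.
- Carotid: (5/7.2) × 2.487 = 1.727. Φ(1.727 − 1.645) = 53% one-sided; Φ(1.727 − 1.96) = 41% two-sided.

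The aorta agrees exactly. The carotid is 4 to 5 points higher because Table 3 implies an SD slightly below 0.4.

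**Step 4: two-sided detectable differences at 80% power.** With 50 per arm, 80% two-sided power needs d ≈ 0.566. Aorta: 0.566 × 0.6 / 3.3 = 10.3%. Carotid: 0.566 × 0.4 / 2.6 = 8.7%.

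**Sensitivity.** Mann-Whitney simulations (normal and log-normal) at 5% give 26–28% (aorta) and 34–37% (carotid) two-sided. SDs taken from the IQRs in Table 3, (4.0 − 2.7)/1.349 = 0.96 and (3.0 − 2.1)/1.349 = 0.67, would give only 13–16% two-sided. They do not reproduce the stated power and are not used.

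**The case against.** The strongest reply is that this is wording and not a miscalculation. The 88% and 99% reproduce on the protocol's basis, and power at two chosen scenarios is ordinary practice. The SAP's clause can also be read conditionally: differences of 10–15%, which lie inside the published range, give this power. TBR is neither the primary outcome (LDL-C) nor the named key secondary (myocardial SUV), and no sample size rests on it. The SAP also promises mean differences with 95% confidence intervals in the secondary section, and an interval would show whether a 5% effect is excluded. Nothing in the documents says that a null TBR result will be read as evidence of no effect.

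Most of this stands, and it limits the severity. It does not restore the missing 5% end of the range, and it does not reconcile a one-sided power with a two-sided criterion.

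Three stronger readings are tempting, and the documents do not support them.

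- A reader might infer that the plan gives no power information below 10%. That is true of the SAP only. Table 3 gives 70% or 80% power at 6.4%, 7.2% and 8.1%, so the protocol already implies under 70% power at 5% for both vessels.
- A reader might infer that the trial would usually miss any effect in the lower part of the range. At 7.5% the two-sided power is 53% and 67%, so detection is more likely than not. At 5%, one-sided carotid power is about even.
- A reader might take Table 3's 7.2% and 9.1% as the limits of what a null result leaves open. Those are one-sided design figures and do not match the SAP's test. What a null result excludes is read from its confidence interval.

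**Conclusion.** The point holds as a minor correction. The SAP misstates the protocol's published range, and its TBR power does not match its own significance criterion. At 5%, power is 39% (aorta) and 49–53% (carotid) one-sided, and 28% and 36–41% two-sided; the upper carotid values come from Table 3's detectable difference. The two bases should not be merged into one range. At 10%, two-sided power is about 78% (aorta), not above 88%, and about 90% (carotid).

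These figures assume 50 evaluable participants per arm, the protocol's SDs, and that the SAP's two-sided criterion covers TBR as well as SUV. They apply to the between-group comparison at 30 days. The documents give no SD for the change in TBR, so nothing here quantifies power for that outcome.

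A reader might infer that the trial is undersized. The documents do not support that, because the size is not justified by TBR and does not need to change.

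**What to change.** Rewrite the SAP's TBR sentence so that it does the following:

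1. Gives the published, clinically relevant range as 5–15%, as in the protocol, and calls 10% and 15% chosen scenarios.
2. Gives two-sided power for 50 per arm at 5%, 10% and 15%: about 28%, 78% and 98% for the aorta; about 36%, 90% and >99% for the carotid. If the one-sided figures from Table 3 are kept as well, label them as one-sided.
3. States the two-sided 80%-power detectable differences: about 10.3% (aorta) and 8.7% (carotid).
4. Says that the figures apply to the 30-day between-group comparison.
5. Says that a non-significant TBR result will be interpreted from its 95% confidence interval.

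This costs a few lines of SAP text and a less favourable stated power. The design, sample size and primary analysis are unaffected.
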